based on recipes derived from various heritage diets. The dietitian will specifically address documented concerns about distrust of online grocery shopping among minoritized groups. The first grocery ordering session will last 60-90 minutes to review principles, place initial orders, and review instructions. Based on prior experience, subsequent sessions, conducted over the phone, last about 30 minutes as participants standardize their orders and become familiar with the intervention. Follow-up calls will increasingly focus on each participant's experience with groceries the prior week, how to optimize food storage and preparation, and exploration of new healthy food items.

The allocation of groceries, like DASH, is designed to be isocaloric (i.e., weight neutral). Calorie needs will be estimated using the Mifflin-St. Jeor estimator based on age, sex, body mass index (BMI), and self-reported physical activity (based on the IPAQ instrument),⁵¹ a validated predictor of resting metabolic rate.¹⁰ The intervention will target a quantity of foods that meet a participant's Calorie needs in addition to up to five additional adults at dinner. The calorie replacements will be categorized based on number of food servings. Groceries will be ordered weekly with the assistance of our study dietitian through Amazon Fresh or Instacart in fixed proportions of grains, vegetables, fruits, low-fat/fat-free dairy, lean meat (fish/poultry), and nuts/beans/legumes to achieve a low sodium (<2,300 mg/d) and high potassium diet modeled after DASH. For example, servings for an adult consuming 14,000 Calories/week (i.e., 2,000 Calories/day) will be sent: 49 servings of grains, 35 servings of vegetables, 35 servings of fruits, 21 servings of fat-free/low-fat dairy, <42 servings of lean meats, and 4-5 servings of nuts, seeds, and legumes, ⁶⁰ 14 servings of healthy fats and oil. See Table 4.1 number of food servings by calorie level. Table 4.2 outlines number of food servings by Calorie level for additional adults at dinner time.

Table 4.1: DASH Eating Plan—Number of Food Servings by Weekly Calorie Level

Table 4.1. DAON Lating I lan—Number of I ood Servings by Weekly Calone Level												
Food Group	8400	9800	11200	12600	14000	16000	18200	21700				
	kcal	kcal	kcal	kcal	kcal	kcal	kcal	kcal				
Grains	28-35	35-42	42	42	42-56	56-70	70-77	84-91				
Vegetables	21-28	21-28	21-28	28-35	28-35	30-37	35-42	42				
Fruits	21-28	21-28	21-28	28-35	28-35	30-37	35-42	42				

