	14-21	14-21	14-21	14-21	14-21	21	21	21-28				
dairy products												
Lean meats, poultry,	21 or	21-28 or	21-28 or	42 or	42 or	42 or	42 or	42-63 or				
and fish	less	less	less	less	less	less	less	less				
Nuts, seeds, legumes	3 per	3 per	3-4 per	4 per	4-5 per	6 per	7 per	7 per				
	week	week	week	week	week	week	week	week				
Fats and oils	7	7	14	14-21	14-21	21	21	28				

Adapted from NHLBI's DASH Eating Plan. https://www.nhlbi.nih.gov/education/dash/following-dash

Table 4.2. Number of Food Servings by Calorie Level to be Increased by the Addition of Adults at Dinner Time

			, ,	4000		, ,	0.400		, ,		
Food Group	800	kcal	(+1	1600	kcal	(+2	2400	kcal	(+3	2 200 keel (14	4.000 keel (15
	adult)		1600 kcal (+2 adults)		adults)			3,200 KGai (+4	4,000 Kcai (+5	

				adults)	adults)
Grains	3 servings/day	6 servings/day	9-10	12-13	15-16
			servings/day	servings/day	servings/day
Fruit	2 servings/day	4 servings/day	4-5 servings/day	6-7	8-9
				servings/day	servings/day
Vegetable	2 servings/day	4 servings/day	4-5 servings/day	6-7	8-9
				servings/day	servings/day
Fat-free or low- fat dairy	9 ,		3 servings/day	4	5
lat daily				servings/day	servings/day
Lean meats,	1-2 oz/day, or	3-4 oz/day, or	6 oz/day, or less	8 oz/day or	9-10 oz/day or
poultry, and fish	less	less		less	less
Nuts, seeds,	1-2 servings per	3-4 per week	1 serving/order	1-2	1.5-2
legumes	order	order		servings/order	servings/order
Fats or oils	1 serving per	2 servings per	3 servings per		
	day	day	day		

Adapted from NHLBI DASH Eating Plan—Number of Food Servings by Calorie Level. Note that children under age 18 years count as 0.5 adults.

Sodium, potassium, and saturated fat are the primary nutrient focuses for GoFresh, (Table 5) modelled after the DASH eating plan.^{6,7,61} Orders will be placed to comply with both absolute milligrams of sodium and potassium per day. Grocery orders will also be required to achieve sodium and potassium density targets adjusted to match participants' caloric intake.

Table 5. Daily Nutrient Targets

Daily Nutrient Targets	GoFresh Plan
Sodium (mg/day)	≤2300
Potassium (mg/day)	≥4700
Saturated fat	7% of total energy
	(~15 g/day)
Ratios	
Na/kcal	<1.1
K/kcal	>2.2

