Intervention Adherence Strategy: Grocery lists will include an extensive range of spices and food items that conform to a DASH dietary pattern (i.e., low sodium, high potassium, reduced added sugars, and reduced saturated fat). Participants will also be given recipes that incorporate a sampling of the groceries on our DASH menu to provide ways to prepare and incorporate foods into their daily life and that are culturally relevant to diverse Black cultural groups. At randomization and during GO calls, participants will be reminded not to eat fast food or at restaurants, which will be monitored. It is possible that participants need to supplement our groceries with their own (e.g., if cooking for others). However, we will ask participants to adhere to our groceries for their own consumption. Participants will be strongly encouraged not to eat out more than once a month, especially not within 2 weeks of the follow-up visit. In addition to grocery orders, the study dietitian will ask participants about food consumption the preceding week, assessing for hoarding, sharing, spoilage, and delivery concerns, as well as providing tips to improve adherence.

Delivery Action Plan:

After the grocery order is placed and delivered, participants will be asked to inform the dietitian if anything is missing from their order through a text, call, or email. Participants will also be asked to inventory any damaged or spoiled items. In addition, the dietitian will receive alerts about items that were not delivered or out of stock. A supplemental order will be placed using an alternative vendor if greater than 25% of the servings targeted within a food group are not available for consumption or if the dietitian feels the participant cannot reach the DASH goals without the missing item(s).

Interventionist Training: The intervention will primarily be delivered by our research dietitians. All staff will participate in three 60-minute sessions that will consist of training in clear communication skills, person-centered care, impact of literacy, oral literacy load, barriers to diet adherence, and the teach-back method. Training will also focus on cultural competence, the role of social determinants of health in health disparities, and the importance of food in Black culture. These sessions will include didactics and role-playing exercises.

Monitoring Adherence

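### From the third extra adult on, the nuts, seeds and legumes row of Table 4.2 contradicts both its own earlier cells and Table 4.1

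*Protocol*

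**What the plan says.** Protocol section 11 sets the size of the grocery order in two steps. Table 4.1 gives the participant's own servings by weekly calorie level. Table 4.2 gives the add-on for other diners; its title says the servings are "to be Increased by the Addition of Adults at Dinner Time". The stated aim is broad: "The intervention will target a quantity of foods that meet a participant's Calorie needs in addition to up to five additional adults at dinner". Section 5 admits households of up to six adults including the participant, so all five add-on columns can come into use.

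Orders are weekly ("Groceries will be ordered weekly with the assistance of our study dietitian"), and the food groups, nuts, beans and legumes among them, are to be bought "in fixed proportions of grains, vegetables, fruits" and so on.

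The row labelled "Nuts, seeds, legumes" in Table 4.2 reads, from one to five extra adults: 1-2 per order, 3-4 per week order, "1 serving/order", 1-2 per order, 1.5-2 per order. In Table 4.1 the same food group is 3-4 per week at 11,200 kcal/week, 6 at 16,000, and 7 at both 18,200 and 21,700.

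The Delivery Action Plan in section 11 calls for a supplemental order if "greater than 25% of the servings targeted within a food group are not available for consumption", or if the dietitian judges that the participant cannot reach the DASH goals without the missing items.

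**The concern.** An add-on for extra diners should not shrink as diners are added, and this row does so without explanation. The unit wording also changes along the row. Table 4.2 fixes quantities that are ordered, so this is an operative figure and not background text.

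If the row is followed as printed, a household with three or more extra adults would be sent fewer servings of this food group than a household with two. The 25% threshold for a supplemental order would be set on that same target, so an order filled to the printed figure would not trip it. Section 7 also plans exploratory analyses of the grocery order sheets stratified by food items, and a pattern by household size created by the table would pass into those. Finally, another team could not reproduce this part of the intervention from a row whose meaning may differ sevenfold according to the unit.

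**Working it through.** **Inputs.** Nuts rows of Tables 4.1 and 4.2, and weekly ordering (all Protocol section 11). Table 4.2 does not label its calories as daily or weekly. Most of its rows are in servings per day, so I take the calories as daily and multiply by 7 to reach the weekly basis of Table 4.1.

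**Check of the daily basis.** Grains at three extra adults: 9-10 per day × 7 = 63-70 per week. The two Table 4.1 columns around 2,400 × 7 = 16,800 kcal/week give 56-70 and 70-77. The basis holds.

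**Nuts, seeds and legumes, servings per week:**

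| Extra adults | kcal/day | kcal/week | Table 4.2 as printed | Table 4.1 | Table 4.2 ÷ Table 4.1 |
|---|---|---|---|---|---|
| 1 | 800 | 5,600 | 1-2 | no column; scaled 3 × 5,600/8,400 = 2.0 | 0.5-1.0 |
| 2 | 1,600 | 11,200 | 3-4 | 3-4 (exact column) | same range |
| 3 | 2,400 | 16,800 | 1 | 6-7 (columns 16,000 and 18,200) | 1/7 to 1/6 |
| 4 | 3,200 | 22,400 | 1-2 | 7 (nearest column, 21,700) | 1/7 to 2/7 |
| 5 | 4,000 | 28,000 | 1.5-2 | no column; scaled 7 × 28,000/21,700 = 9.0 | 0.17-0.22, extrapolated |

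Linear interpolation at 16,800 gives 6 + (800/2,200) × 1 = 6.36, so the ratio there is 1/6.36 = 0.16.

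**Is it only this row?** Other cells at three extra adults, per week, against the two bracketing Table 4.1 columns:

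- Dairy: 3 × 7 = 21, against 21.
- Fats and oils: 3 × 7 = 21, against 21.
- Lean meat: 6 oz × 7 = 42 oz, against 42 or less (taking one ounce as one serving, an assumption).
- Fruit, and likewise vegetables: 4-5 × 7 = 28-35, against 30-42; overlapping, slightly low.
- Nuts, seeds and legumes: 1, against 6-7.

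**Proportions.** In Table 4.2, nuts to grains is 3/42 to 4/42 = 0.071-0.095 at two extra adults, and 1/70 to 1/63 = 0.014-0.016 at three. The stated fixed proportions are not kept.

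**Effect on the whole order, as printed.** For an illustrative participant at 14,000 kcal/week (4-5 servings of their own):

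- two extra adults: 4+3 to 5+4 = 7-9 servings for three diners;
- three: 4+1 to 5+1 = 5-6 for four;
- four: 4+1 to 5+2 = 5-7 for five;
- five: 4+1.5 to 5+2 = 5.5-7 for six.

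**Unit-slip check.** Read the last three cells as per day: 1 × 7 = 7; 1-2 × 7 = 7-14; 1.5-2 × 7 = 10.5-14 per week. Against 6.36, 7.23 (7 × 22,400/21,700) and 9.03 these are about 1.1, 0.97-1.9 and 1.2-1.6 times Table 4.1, and the fall disappears. The same reading of the first two cells would give 7-14 and 21-28, or 3.5-7 and 5.3-9.3 times Table 4.1. A slip of this kind would therefore have to begin at the third adult. This tests consistency only; it does not show which entry is right.

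**The case against.** A reader might infer that large households are under-supplied, at about one-seventh of what Table 4.1 implies. The documents do not support that. The unit-slip reading removes the fall and brings the three cells to about the Table 4.1 level or above it, and nothing in the documents shows what was ordered. One-seventh also fits only three extra adults and the low end of four; the top of four is two-sevenths, and five can be compared only by extrapolation. Nor may one assume that Table 4.1 is the correct table.

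A reader might also infer that the error weakens the DASH arm or blurs the family-size subgroup. Several features speak against a large effect:

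- Only one food group shows the fall among the rows that could be compared. The dairy cells for one and two extra adults and the fats cells for four and five could not be read.
- The participant's own allotment comes from Table 4.1 whatever the household size, and every order must still meet the sodium and potassium targets of Table 5.
- The dietitian asks each week about sharing and leftovers, and the supplemental-order rule has a discretionary limb besides the 25% threshold. That limb concerns missing items, however, and would not correct a table.
- The SAP subgroup (section 3.4, subpopulations) compares single households with all others, so it does not isolate those with three or more extra adults. Their number is not given.

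These points limit the consequence. They do not remove the contradiction, because no other text says which figures apply.

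**Conclusion.** The contradiction stands. As printed, with one order per week, the nuts, seeds and legumes add-on drops from 3-4 servings at two extra adults to 1 at three, and does not exceed 2 at four or five. Against Table 4.1 it is 1 versus 6-7 at three and 1-2 versus 7 at four, although the two tables agree exactly at two. Either the values or the units from the third adult onward are wrong.

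This rests on weekly orders, which the protocol states, and on daily calories in Table 4.2, which the grains row confirms. Under-supply is conditional on the row being followed as printed. No effect on SBP, the DASH index or a subgroup can be estimated from the documents; an effect on SBP is probably small. Sample size and power do not depend on this point.

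**What to change.** Reconcile the nuts, seeds and legumes row of Table 4.2 with Table 4.1 and with its own cells for one and two extra adults, and state one unit across the row. Carry the reconciled row into the order worksheet and into the target used for the 25% supplemental-order threshold. For orders already placed for households with three or more extra adults, record which figures were used. The study team decides which figures stand.

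The cost is one table correction, one worksheet update and a look back at the order sheets of the affected households. Depending on how the row is resolved, the contents of their later orders may change slightly.

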5. STUDY POPULATION AND ELIGIBILITY

Eligibility criteria are summarized below. This trial focuses on hypertension in the setting of no active hypertension medication use. We will include families with less than or equal to 6 adults (including the index person) at dinner time to allow for sharing (a child less than 18 is counted as half an adult), while maintaining adequate food for the study participant.

Inclusion criteria

- Age 18 to 100 years
- Self-reported/self-identified as Black or African American
- Resting systolic blood pressure of 120 to <150 mm Hg and diastolic blood pressure <100 mm Hg based on the cumulative average across three pre-randomization visits
- Residence in communities identified by the Massachusetts Department of Public Health as Suffolk County (Boston area) food deserts: Brighton, Chelsea, Dorchester, Hyde Park,

- Mattapan, Revere, Roxbury, Winthrop, or East Boston, Malden, Jamaica Plain, Roslindale, and Everett.
- Able to receive home-delivered groceries or pick them up at a convenient location and willing to eat only the groceries provided over a 12-week period
- Have access to refrigeration, cooking appliances, and Wi-Fi/cellular service
- Have access to mobile device or computer to be able to conduct grocery orders via video conference or by phone
- Willing and able to complete required measurement procedures

Exclusion criteria

Laboratory Exclusions:

- Serum potassium ≥5.0 mmol/L or <3.5 mmol/L
- Estimated glomerular filtration rate (eGFR) <30 mL/min per 1.73 m² by the Chronic Kidney Disease Epidemiology Collaboration (CKD-EPI) equation
- Hemoglobin A1c ≥6.5%

Medication Exclusions:

- Any use of medications that lower blood pressure or medications intended for hypertension treatment (including antihypertensives taken for non-hypertension purposes) within the last 6 months
- Unstable doses (i.e., a change in the 2 months prior to screening or randomization) of the following:
 - Sodium-glucose co-transporter 2 (SGLT2) inhibitors
 - Stimulants
 - Inhaled or oral medications for asthma or chronic obstructive pulmonary disease (COPD)
 - Hormone replacement therapy or thyroid hormone
 - Weight-increasing psychotropic agents, including antipsychotic agents, lithium, and mirtazapine
- Use of any of the following medications:
 - o Potassium supplement, except if part of a multivitamin
 - Warfarin (Coumadin)
 - Chronic oral corticosteroid (intermittent use is okay)
 - Weight loss medications (including GLP-1 receptor agonists)

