10. RANDOMIZATION AND MASKING

After screening, consenting participants will be 1:1 randomized to the DASH grocery or self-directed arm using web-based, password-protected, randomization software following a permuted block scheme (sizes of 2, 4, or 6). Participants and staff directly administering the intervention will be informed of randomization assignments, but they will be masked to study results until after the study is complete. Meanwhile, staff who perform clinic assessments and the study investigators will be masked to randomization assignments.

The randomization schemes will be generated by the Beth Israel Deaconess Medical Center biostatistician using permuted block methods. Randomly-varying block sizes of 2, 4 and 6 will be used. Randomization will be stratified by baseline systolic blood pressure: 120-139 mm Hg or 140-<150 mm Hg (stage II hypertension) in order to ensure balanced treatment assignments in each BP group.⁵⁹ Details of the block sizes will be concealed from study staff and investigators and generated prior to the study and added to the data management system/REDCap for digital randomization. Randomization tables will be uploaded to REDCap corresponding to the two BP strata. A designated staff member that is unblinded (most commonly our dietitian interventionist) will randomize participants by clicking on a digital randomization button in REDCap after informed consent, confirmation of eligibility, reviewing details of the intervention, and signing an intervention understanding form. This will be performed in a private location in the clinical research center away from other study staff. Once the assignment is revealed in REDCap, this information will be shared with the study dietitian, who will provide instructions pertinent for each intervention phase. Intervention assignment will not be shared with research coordinator or assistants performing data assessments or with study investigators. Other members of the study team will not be able to access this assignment information in REDCap. Study personnel and investigators will not be unmasked until follow-up and all data collection are completed.

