This trial has minimal risks. Nevertheless, participant safety is a priority. We will monitor safety as described in this section. Prior to enrollment in this study, we will screen potential participants to ensure it is safe for them to participate. Substantial effort has been made to identify and minimize potential risks where possible and to exclude participants for whom participation in this study might incur undue risk (see eligibility criteria for full details on exclusions). Once enrolled, if a participant develops an adverse event or other medical problem, the safety of continuing in the study will be determined by study clinicians during a weekly trial meeting.

At the beginning of the study, we will ask participants to provide the information to their usual healthcare provider. If they do not have a usual healthcare provider, we will provide them with resources to identify one. We will provide a printed provider letter participants can give to their healthcare provider outlining their involvement in the study. With the participant's permission, we may also contact their healthcare providers for urgent medical issues that may arise during the study as described in more detail below.

Potential Risks

Risks related to breaches of confidentiality

As with any medical information, there is the risk of psychological distress if personal health information is not kept confidential. To minimize the risk of a breach of confidentiality, all researchers involved are trained in HIPAA compliance. Data will be de-identified and stored on a secure, password-protected server hosted by computers in locked offices that only the research study team can access. All paper records associated with this study will be stored in a locked file cabinet in a locked room. Biospecimens will be stored using de-identified labels and kept in a secure location within BIDMC. Data are only used in aggregate and no identifying characteristics of individual participants will be published.

Identifying participants with food insecurity

At screening visits, we will assess food insecurity. Although potential participants who are deemed extremely food insecure will not be eligible for participation, all participants will receive locally adapted information about available resources in the event they develop food insecurity during the study.

Risks related to phlebotomy

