Blood work will be done at designated study visits. Common but less serious risks of phlebotomy include minor bleeding, bruising, swelling and pain at the phlebotomy site. Rare but more serious risks from phlebotomy include vasovagal syncope or infection. There is no alternative to phlebotomy for measuring serum biomarkers and all of these risks exist in the course of routine medical care. To minimize any additional risk, the frequency of phlebotomy is kept to a minimum and will be drawn by trained staff using aseptic techniques.

Risks related to dietary changes

The diet intervention is patterned after standard recommendations for a healthy diet and should pose minimal risk for participants. Nevertheless, any dietary changes can cause some symptoms, and there may be a risk of a reaction to new food types. Common reactions include rash or hives, itching or watery eyes, wheezing or difficulty breathing, and itching and/or swelling of the mouth and throat. Participants might experience mild gastrointestinal discomfort related to a diet that has higher amounts of fiber, dairy, fresh fruits and vegetables than they usually consume. These symptoms are generally mild and resolve quickly.

Participants will be monitored for these reactions and their grocery orders can be modified as needed. Severe allergies or reactions to new foods should be rare and care will be taken to avoid any known food allergens. Should a reaction occur, we will recommend that the participant avoids the food item and seeks medical care.

Risks related to family members

Participants assigned the dietitian-directed intervention will be provided a food safety handout for family members that might eat some of the groceries. This handout has information about allergies, food intolerance, and food recalls.

Risks related to food recalls or food storage issues

We will regularly monitor Amazon Fresh and Instacart for food recalls that might impact participants. We will notify participants of any recalled products within 2 business days of discovery.

Identifying patients with high blood pressure (hypertension)

We anticipate that the intervention will decrease participant's BP. However, if we discover unusually high blood pressure at our study visits, we will implement safety procedures and BP thresholds that require a response.

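### High-potassium groceries are sized to feed up to five more adults at dinner, but the family safety handout, as described, does not mention potassium or kidney disease

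*Protocol*

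**What the plan says.** Sharing the food is part of the design. Protocol section 5 states: "We will include families with less than or equal to 6 adults (including the index person) at dinner time to allow for sharing", with a child under 18 counted as half an adult. Section 11 sizes each order to the participant's own calorie needs "in addition to up to five additional adults at dinner", and Table 4.2 lists the servings to add for each extra diner. The orders aim at a DASH-type diet low in sodium and high in potassium. Table 5 sets the potassium targets at 4700 mg/day or more and above 2.2 per kcal.

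Section 12 acknowledges that the groceries contain more potassium than Americans usually eat. It says potassium should stay within the normal range in healthy people, and it sets action levels for hyperkalemia found in participants.

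For relatives, section 12 (Risks related to family members) offers one measure. Participants in the grocery arm "will be provided a food safety handout for family members that might eat some of the groceries", and on its content the protocol says: "This handout has information about allergies, food intolerance, and food recalls".

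**The concern.** The protocol treats high potassium as a safety matter for enrolled participants but describes no matching precaution for the other people it plans to feed. Relatives are not screened. One of them could have severe kidney disease, known high potassium or a potassium supplement, and the leaflet as described gives that person no reason to check with a clinician before eating these dinners regularly for 12 weeks. What is at stake is household safety alone.

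**Working it through.** There is no plan figure to reproduce. The check sets the participant and household safeguards side by side and then sizes the extra food.

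**Safeguards described in the protocol**

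| Safeguard | Participant | People sharing dinner |
|---|---|---|
| Kidney function at entry | Excluded if "Estimated glomerular filtration rate (eGFR) <30 mL/min per 1.73" m² (section 5) | None described |
| Serum potassium at entry | Excluded if "Serum potassium ≥5.0 mmol/L", or if below 3.5 (section 5) | None described |
| Potassium supplements | Excluded unless part of a multivitamin (section 5) | None described |
| Laboratory monitoring | Serum creatinine and potassium at SVa, FV1a and FV2a (section 7) | None described |
| Action levels | Hyperkalemia, 5.5 mEq/L or more (section 12) | None described |
| Information | Curriculum module 3 on sodium and potassium (section 11, Table 3) | Leaflet on allergies, intolerance and recalls (section 12) |

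Section 12 (Safety Monitoring) gives the general purpose of the exclusions, which is to keep out people whom participation could put at undue risk. It gives no reason for each criterion. The argument does not need one, because section 12 separately treats high potassium as something to detect and act on.

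**Extra food ordered for household members**

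Inputs: the fruit and vegetable rows of Table 4.2, in servings per day. The two rows are identical: 2 for one added adult, 4 for two, 4–5 for three, 6–7 for four and 8–9 for five.

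Formula: (fruit + vegetable servings per day) ÷ added adults.

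- One added adult: (2 + 2) / 1 = 4.0
- Two: (4 + 4) / 2 = 4.0
- Three: (4 + 4) / 3 = 2.7 to (5 + 5) / 3 = 3.3
- Four: (6 + 6) / 4 = 3.0 to (7 + 7) / 4 = 3.5
- Five: (8 + 8) / 5 = 3.2 to (9 + 9) / 5 = 3.6

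The range is 2.7 to 4.0 servings per added adult per day. For a child at half an adult it is about 1.3 to 2.0.

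I do not convert these servings to milligrams of potassium. The density target in section 11 is tied to the participant's own calorie intake, and Table 4.2 sets no potassium target for the added food.

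**The case against.** The strongest reply is that this argues from a one-sentence summary of a leaflet nobody outside the study has seen. Listing three topics does not mean there are only three. Section 10 also has participants randomized after "reviewing details of the intervention, and signing an intervention understanding form", and that form or the consent pages may already warn about potassium. This stands, and it limits the point to what section 12 describes.

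Second, relatives' exposure is not established. The servings are ordered rather than eaten, and the dinner replaces another meal. Section 11 allows participants to buy their own food when cooking for others. The food is ordinary retail groceries following standard healthy-diet advice. All of this stands, and it is why no harm is quantified.

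Third, the serum potassium criterion has a lower limit as well, so it may be a general electrolyte screen rather than a precaution specific to this diet. That is fair, but the statements on potassium in section 12 remain.

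Fourth, the dietitian asks about sharing on the ordering calls, and module 3 teaches participants about potassium. These are points of contact through which a warning could be given. Neither is described as telling relatives with kidney disease anything, so neither closes the gap.

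**Conclusion.** The concern holds in its narrow form. The trial deliberately supplies high-potassium food in quantities meant for sharing, and the one family safeguard the protocol describes leaves out potassium and kidney disease. This is an optional, low-cost improvement, held with medium confidence.

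The only size the documents support is 2.7 to 4.0 ordered fruit and vegetable servings per added adult per day. Net added potassium and the number of vulnerable relatives cannot be derived. The conclusion rests on the leaflet's content being as section 12 describes it. If a warning already exists in the leaflet or the understanding form, the remaining defect is an incomplete description. The primary analysis and the safety of enrolled participants are not affected.

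**What to change.** Add a short paragraph to the leaflet, worded by the study clinicians. It should say that the groceries are chosen to be high in potassium, and that household members with severe kidney disease, known high potassium or a potassium supplement should ask their clinician before sharing them regularly. Reflect this in the section 12 description. At the first ordering session, have the dietitian confirm that the leaflet reached those who share dinner. If the leaflet or the understanding form already says this, only section 12 needs updating.

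The cost is one paragraph, one check in a session that already lasts 60–90 minutes, and a minor IRB amendment. The downside is that some relatives may choose not to share the food. If deliveries have already ended under the section 16 timeline, the wording could still be considered for the parallel trial in treated hypertension (section 15), which uses a similar intervention.
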